6.4.2 Patient-Reported Outcomes

Scale scores for the Haemo-QoL-SF and the Haem-A-QoL will be calculated for each assessment, with change scores being examined for the assessments over the course of 24 weeks. These will be summarized descriptively.

The proportion of patients preferring emicizumab after 17 weeks of treatment will be presented along with the reasons for that choice. Summary statistics of the number of days away from school and days hospitalized will be presented.

6.5 SAFETY ANALYSES

The safety analyses population will be based on all patients who received at least one administration of emicizumab. Safety will be assessed through descriptive summaries of adverse events, laboratory test results (serum chemistry and hematology including complete blood count with differential and platelet counts), ECGs, vital signs, ADAs, and de novo anti-FVIII inhibitors.

To evaluate the overall safety of emicizumab, the incidence of adverse events will be summarized and presented by System Organ Class mapped term, appropriate thesaurus level, and toxicity grade.

For clinical laboratory data, summary statistics will be presented. In addition, shift tables describing changes from baseline will be presented using the WHO toxicity grading scale (WHO 2003).

6.6 PHARMACOKINETIC ANALYSES

PK Run-In Cohort

PK parameters of emicizumab will be estimated using non-compartmental methods after the first and the sixth injection and include:

- T_{max} : Time to maximum observed plasma concentration
- C_{max} : Maximum observed plasma concentration
- AUC_{τ} : Area under the plasma concentration–time curve over a dosing interval
- AUC_{0-inf} : Area under the plasma concentration–time curve between time zero (predose) extrapolated to infinity (only for the first injection)
- $t_{1/2}$: Apparent terminal half-life
- CL/F and CL_{ss}/F : Apparent Clearance

Concentration data and calculated PK parameters for emicizumab will be presented in individual listings, summary tables (including descriptive statistics: mean, geometric means, medians, ranges, standard deviations, and coefficients of variation) and graphs (including concentration versus time plots on linear and semi-logarithmic scales) as appropriate.

Expansion Cohort

For all patients, predose (trough) plasma concentrations of emicizumab will be presented descriptively, including arithmetic and geometric means, median, range, standard deviations, and coefficients of variation.

Nonlinear mixed effects modeling will be used to analyze the dose-concentration-time data of emicizumab following SC administration. Population PK parameters, such as clearance and volume of distribution, will be estimated, and the influence of various covariates, such as age, gender, and body weight, on these parameters will be investigated graphically. Secondary PK parameters, such as area under the curve, will be derived from individual post-hoc predictions. Data may be pooled with data from previous Phase I/II studies and completed Phase III studies. These analyses will be reported in a dedicated report.

6.7 IMMUNOGENICITY ANALYSES

The immunogenicity analyses will include patients with at least one predose and one postdose ADA assessment.

The numbers and proportions of ADA-positive patients and ADA-negative patients during both the treatment and follow-up periods will be summarized. Patients are considered to be ADA positive if they are ADA negative at baseline but develop an ADA response following study drug administration (treatment-induced ADA response), or if they are ADA positive at baseline and the titer of one or more post-baseline samples is at least 4-fold greater (i.e., ≥ 0.60 titer units) than the titer of the baseline sample (treatment-enhanced ADA response). Patients are considered to be ADA negative if they are ADA negative at baseline and all post-baseline samples are negative, or if they are ADA positive at baseline but do not have any post-baseline samples with a titer that is at least 4-fold greater than the titer of the baseline sample (treatment unaffected).

The relationship between ADA status and safety, efficacy, PK, and biomarker endpoints will be analyzed and reported descriptively via subgroup analyses.

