As of *May 2019*, in the ongoing Phase III Study BH29884 (adolescent and adult patients with hemophilia A with FVIII inhibitors), thrombotic microangiopathy (TMA) was observed in 3 patients receiving emicizumab and bypassing agents; and 2 cases of thromboembolic events were observed in 2 patients receiving emicizumab and bypassing agents. *In addition, 1 patient experienced a serious adverse event of acute myocardial infarction in Phase IIIb study MO39129, a single-arm study of prophylactic emicizumab in patients with congenital hemophilia A who have persistent inhibitors against FVIII.* For more details, refer to Sections [5.1.2.3](#) and [5.1.2.4](#) and the current RO5534262 (Emicizumab) Investigator's Brochure.

Emicizumab exhibited linear PK after single SC administration. Following single SC injection, its mean elimination $t_{1/2}$ (4–5 weeks) was similar to that of other human IgG antibodies. Furthermore, comparison of PK profiles between Japanese and Caucasian

healthy volunteers did not reveal racial differences. In patients with hemophilia A, emicizumab trough plasma concentrations increased in a dose-proportional manner with weekly dosing to achieve a plateau after approximately 12 weeks in the first two dosing groups, in which a loading dose was administered, and after approximately 24 weeks in the highest dose group, in which no initial loading dose was administered.

Until the cutoff in April 2018 in four Phase III clinical trials of emicizumab (Studies BH29884, BH29992, BH30071, and BO39182), <5% of patients tested positive for anti-drug antibodies (ADAs) to emicizumab and <1% of patients developed ADAs with neutralizing potential (based on declining pharmacokinetics). A similar safety profile was observed in patients, irrespective of the presence of ADAs. One patient who developed ADAs with neutralizing potential experienced loss of efficacy after 5 weeks of treatment and discontinued emicizumab treatment. For further updated information, consult the current RO5534262 (Emicizumab) Investigator's Brochure.

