2.2.2 Safety Objectives

The safety objectives of this study are to evaluate the overall safety of emicizumab given Q4W in patients with hemophilia A based on the following endpoints:

- The incidence and severity of adverse events
- The incidence and severity of thromboembolic events
- Changes in physical examination findings and vital signs
- Incidence of laboratory abnormalities
- Incidence and severity of injection-site reactions
- Incidence of adverse events leading to drug discontinuation
- Incidence of severe hypersensitivity, anaphylaxis, and anaphylactoid events
- Incidence of thrombotic microangiopathy
- The incidence and clinical significance of anti-emicizumab antibodies
- The incidence of de novo development of FVIII inhibitors (non-inhibitor population)

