4. MATERIALS AND METHODS

4.1 PATIENTS

Approximately 46 patients with congenital hemophilia A previously treated with either FVIII or bypassing agents will be enrolled in the study (6 patients in the PK run-in phase and 40 patients in the expansion phase).

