2.4 DETERMINATION OF SAMPLE SIZE

The sample size of 6 patients for the PK run-in cohort is considered appropriate to assess pharmacokinetics and safety to allow for an informed decision to open the subsequent expansion cohort with 40 additional patients. One additional patient was recruited in the run-in cohort to ensure that the predefined number of patients (6) complete 6-weeks treatment for required PK data in order to enable a decision for opening the expansion cohort, in case of withdrawal.

The overall sample size of 40 patients in the expansion cohort is based primarily on clinical considerations taking into account the limited number of patients with hemophilia A. It is expected that a sample size of 40 patients would, nonetheless, provide statistically robust point estimates with meaningfully narrow CIs.

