4.7.3 Laboratory Data

For clinical laboratory data that were collected from local laboratories, summary statistics will be presented in International System of Units (SI). Laboratory data not collected in SI units will be converted to SI units as applicable. In addition, shift tables describing changes from baseline will be presented using the WHO toxicity grading scale.

Data on the impact of immunogenicity (anti-emicizumab antibodies) on safety, efficacy, and/or clinical pharmacology and pharmacokinetics will be summarized using standard language/terminology ([Shankar et al. 2014](#)).

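### With about two ADA-positive patients expected, no onset split and no neutralizing category, the ADA subgroup comparison cannot rule out an effect on bleeding or a moderate loss of exposure

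*Protocol*

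**What the plan says.** Protocol 2.2.2 lists "The incidence and clinical significance of anti-emicizumab antibodies" among the safety endpoints. Protocol 6.7 labels each patient positive (treatment-induced or treatment-enhanced at any post-baseline sample) or negative. It then states that "The relationship between ADA status and safety, efficacy, PK, and biomarker endpoints will be analyzed and reported descriptively via subgroup analyses". The synopsis in SAP Appendix 1 repeats this text.

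The SAP body adds one sentence, in 4.7.3: "Data on the impact of immunogenicity (anti-emicizumab antibodies) on safety, efficacy, and/or clinical pharmacology and pharmacokinetics will be summarized", followed by a reference to standard terminology and a cited paper. ADA status is not among the main subgroups in SAP 4.5.3. SAP 2.3.1 starts each patient's efficacy period at the first dose. Neither analysis section defines an ADA onset date, a before/after comparison or a neutralizing category.

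Protocol 1.2.2 gives pooled experience from four Phase III trials, this one included: "<5% of patients tested positive for anti-drug antibodies (ADAs) to emicizumab and <1% of patients developed ADAs with neutralizing potential", with neutralizing potential judged from declining pharmacokinetics. It adds: "One patient who developed ADAs with neutralizing potential experienced loss of efficacy after 5 weeks of treatment and discontinued emicizumab treatment".

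**The concern.** A two-group table answers this objective only if both groups are large enough and the label matches the period at risk. Here one group may hold two patients or fewer. The ABR attached to each positive patient mixes time before and after the antibody appeared. A patient whose antibodies clear the drug sits in the same row as one whose antibodies do nothing.

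Similar columns in such a table carry almost no information, yet are easily read as reassurance. Collecting more data on antibody development is a stated reason for the Version 5 extension, so the report will be expected to say something on it. The informative evidence is the course of concentration, modified aPTT and bleeds within each positive patient around onset, and no planned output brings these together.

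**Working it through.** The plan states no power or precision figure for this analysis, so there is none to reproduce.

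**Inputs from the documents**
- Patients: "Approximately 46 patients with congenital hemophilia A previously treated with either FVIII or bypassing agents will be enrolled in the study" (Protocol 4.1: 6 run-in, 40 expansion). SAP 2.4 adds a seventh run-in patient ("One additional patient was recruited in the run-in cohort"), giving 47. The cohorts are analysed separately (Protocol 6, SAP 2.5), so 40 is the main denominator.
- Ceilings of 5% positive and 1% neutralizing (Protocol 1.2.2).
- 24 weeks = 168/365.25 = 0.460 years.

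**Assumed, because the documents give no figure**
- ABR in ADA-negative patients 1–5; negative binomial dispersion k = 1–4.
- Trough CV 30–50%. Protocol 3.3.1 gives simulated Cmax 78.1 ± 20.9 (CV 27%) and AUC 1570 ± 447 (CV 28%), but no trough SD.

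**1. Expected counts**
- Positive at 5%: 40 × 0.05 = 2.0 (2.35 of 47). P(0 or 1) = 0.95^40 + 40 × 0.05 × 0.95^39 = 0.1285 + 0.2706 = 0.399. For 47 it is 0.31.
- Neutralizing at 1%: 0.40 of 40, 0.47 of 47. P(none) = 0.99^40 = 0.67 and 0.99^47 = 0.62.

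**2. What an observed bleed-rate ratio of 1 would mean, 2 versus 38 patients**

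With m expected bleeds per patient, var(log ratio) ≈ (1/m + k)(1/2 + 1/38).
- ABR 2.5, k = 2: m = 2.5 × 0.460 = 1.15. The variance is 2.870 × 0.526 = 1.510, SE 1.229, and exp(1.96 × 1.229) = 11.1. The 95% interval around 1 runs from 0.09 to 11.
- Over the assumed ranges the upper limit goes from 5.5 (ABR 5, k = 1) to 34 (ABR 1, k = 4).
- Longer follow-up helps little while two patients are positive. As m grows, the variance falls only to 0.526k, which leaves upper limits of about 4.1 (k = 1) to 17 (k = 4).

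**3. Dilution of a true fourfold rate**
- Onset halfway through 24 weeks: 0.5 × 1 + 0.5 × 4 = 2.5. Onset at 5 of 24 weeks: 5/24 × 1 + 19/24 × 4 = 3.4.
- One of two positive patients affected, from halfway: (1 + 2.5)/2 = 1.75.

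**4. Simulated bleeds, 2 versus 38, 24 weeks**

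The gauge is how often the 95% interval excludes 1. It measures visibility and is not a planned test.

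| True ratio | Both affected throughout | One of two, half the time |
|---|---|---|
| 2 | 1–9% | 0–3% |
| 4 | 5–36% | 1–6% |
| 10 | 20–77% | 4–26% |

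For ratio 4 with one of two affected for half the time, the ADA-positive rate is no higher than the ADA-negative rate in 37–57% of runs.

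**5. Simulated troughs (log scale), one of two positive patients affected**

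| Loss in that patient | At a post-onset visit | Averaged, half the time affected |
|---|---|---|
| 50% | 16–33% | 6–9% |
| 90% | 84–99% | 13–26% |

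Shown alone after onset, a patient with a 90% loss lies below every ADA-negative value in 99–100% of runs. With a 50% loss the figure is about 27–58%.

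**The case against.** Several points on the other side stand.

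- **Exposure.** SAP 4.6.2 summarizes troughs at each timepoint. A reader might infer that any real loss of exposure would be hidden. That goes too far: split by ADA status, a near-complete loss in one of two positive patients would usually be visible after onset, at least in the geometric means.
- **No test is planned.** Protocol 6 and SAP 4.5 are descriptive, and neither document says a no-effect conclusion will be drawn. SAP 4.5.3 warns about small subgroups, although ADA status is not in that list. The interval results above therefore gauge how much the table can show and are not error rates of a planned test.
- **Silence.** Neither document states that pre-onset time counts as ADA-positive or that neutralizing cases are pooled. For the ABR the first follows from the patient-level label and an efficacy period starting at first dose. The second is inferred from the missing category. The paper cited in SAP 4.7.3 is not available here, so it can be neither credited with these rules nor assumed to lack them.
- **Protocol 1.2.2.** The sentence "A similar safety profile was observed in patients, irrespective of the presence of ADAs" might be read as the conclusion this plan will generate. It concerns safety only, pools four trials and is not an output of Protocol 6.7. The same paragraph reports the neutralizing case individually.
- **Proportion neutralizing.** Dividing under 1% by under 5% might suggest one in five positive patients is neutralizing. A quotient of two upper bounds estimates nothing.
- **Listings.** Bleeds are listed per patient (SAP 4.5.1), and population PK gives individual predictions. A single case could be traced, but no ADA marker is specified for the bleed listing. Individual concentration listings are specified only for the run-in cohort, and the covariates named for the population model are age, gender and body weight.

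**Conclusion.** The point holds for bleeding and for moderate loss of exposure. With at most about 2 ADA-positive patients expected among 40, and about 0.4 neutralizing, the planned comparison cannot support a statement that antibodies do not affect bleeding, or that they cause no loss of exposure of around 50%. It does not hold for near-complete loss of exposure, which by-visit troughs would usually reveal.

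The counts assume that the pooled ceilings apply to this trial. The bleed and trough figures rest on the assumed ABR, dispersion and CV ranges, and the conclusion is the same throughout them. The key efficacy estimate is unaffected. The gap concerns one named safety objective and is cheap to close.

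**What to change.** Keep the subgroup table and add the following to SAP 4.7.3 and Protocol 6.7.

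1. For each ADA-positive patient, a profile over time of emicizumab concentration, modified aPTT, treated bleeds, injection-site reactions and hypersensitivity events, with the first ADA-positive sample marked. For treatment-enhanced patients, mark the first sample meeting the fourfold criterion.
2. Trough, ABR and adverse event counts split into time before and time from that sample.
3. Separate reporting of positive patients whose concentration declines, the criterion Protocol 1.2.2 already uses for neutralizing potential.
4. ADA incidence with an exact 95% interval, and a note that absence of a visible difference with so few positive patients is not evidence of no impact.

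No new data are needed. In the expansion cohort, ADA, PK and biomarker set 1 samples share the visits at Weeks 5, 9, 13, 17, 21 and 25 and every 12 weeks thereafter (Protocol Appendix 2), and bleeds are dated (Appendix 1). Onset will be known only to within those sampling intervals.

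The cost is a short SAP paragraph, a few extra outputs and the loss of any general claim, from this study alone, that results hold regardless of ADA status. The change cannot create cases: at the 1% ceiling there is a 62–67% chance of no neutralizing patient.

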6.8 EXPLORATORY ANALYSES

PD parameters (e.g., aPTT, parameters derived from thrombin generation, FVIII activity) will be presented using summary statistics, including arithmetic and geometric means, median, range, standard deviations, and coefficients of variation.

6.9 INTERIM ANALYSIS

6.9.1 Planned Interim Analysis

An analysis of pharmacokinetics and safety will occur when the first 6 patients have been on treatment for 6 weeks. On the basis of the results for pharmacokinetics and safety (e.g., \geq lower limit of 95% CI of the predicted mean PK profile, no severe unexpected safety findings), the study will proceed with the expansion cohort.

This analysis will be conducted by a Roche internal group of representatives from Clinical Pharmacology, Clinical Science, Clinical Safety and Statistics; no formal IMC will be set up.

6.9.2 Optional Interim Analysis

Additional interim data reviews may be performed at various timepoints to support regulatory submissions.

7. DATA COLLECTION AND MANAGEMENT

7.1 DATA QUALITY ASSURANCE

The Sponsor will be responsible for data management of this study, including quality checking of the data. Data entered manually will be collected via EDC through use of eCRFs. Sites will be responsible for data entry into the EDC system. In the event of

discrepant data, the Sponsor will request data clarification from the sites, which the sites will resolve electronically in the EDC system.

The Sponsor will produce an EDC Study Specification document that describes the quality checking to be performed on the data. Data will be sent directly to the Sponsor, using the Sponsor's standard procedures to handle and process the electronic transfer of these data.

eCRFs and correction documentation will be maintained in the EDC system's audit trail. System backups for data stored by the Sponsor and records retention for the study data will be consistent with the Sponsor's standard procedures.

7.2 ELECTRONIC CASE REPORT FORMS

eCRFs are to be completed through use of a Sponsor-designated EDC system. Sites will receive training and have access to a manual for appropriate eCRF completion. eCRFs will be submitted electronically to the Sponsor and should be handled in accordance with instructions from the Sponsor.

All eCRFs should be completed by designated, trained site staff. eCRFs should be reviewed and electronically signed and dated by the investigator or a designee.

At the end of the study, the investigator will receive patient data for his or her site in a readable format on a compact disc that must be kept with the study records. Acknowledgement of receipt of the compact disc is required.

7.3 ELECTRONIC PATIENT-REPORTED OUTCOME DATA

Patient-reported data will be collected electronically with use of electronic devices. The electronic device is designed for entry of data in a way that is attributable, secure, and accurate, in compliance with FDA regulations for electronic records (21 Code of Federal Regulations, Part 11). The data will be transmitted electronically in real-time to a centralized database at the vendor of the electronic handheld devices. The data from the electronic devices are available for view access only via secure access to a Web portal provided by the vendor. The Sponsor will have view access only. Regular data transfers will occur from the centralized database at the vendor to the database at the Sponsor. The Sponsor will receive all data entered by patients on the electronic handheld devices and all relevant study documentation.

Once the study is complete, the data, audit trail, and study and system documentation will be archived. The investigator will receive patient data for the site in both human- and machine-readable formats on an archival-quality compact disc that must be kept with the study records as source data. Acknowledgement of receipt of the compact disc is required. In addition, the Sponsor will receive all data in a machine-readable format on a compact disc.

7.4 SOURCE DATA DOCUMENTATION

Study monitors will perform ongoing source data verification to confirm that critical protocol data (i.e., source data) entered into the eCRFs by authorized site personnel are accurate, complete, and verifiable from source documents.

Source documents (paper or electronic) are those in which patient data are recorded and documented for the first time. They include, but are not limited to, hospital records, clinical and office charts, laboratory notes, memoranda, electronic handheld device records, evaluation checklists, pharmacy dispensing records, recorded data from automated instruments, copies of transcriptions that are certified after verification as being accurate and complete, microfiche, photographic negatives, microfilm or magnetic media, X-rays, patient files, and records kept at pharmacies, laboratories, and medico-technical departments involved in a clinical study.

Before study initiation, the types of source documents that are to be generated will be clearly defined in the Trial Monitoring Plan. This includes any protocol data to be entered directly into the eCRFs (i.e., no prior written or electronic record of the data) and considered source data.

Source documents that are required to verify the validity and completeness of data entered into the eCRFs must not be obliterated or destroyed and must be retained per the policy for retention of records described in Section 7.6.

To facilitate source data verification, the investigators and institutions must provide the Sponsor direct access to applicable source documents and reports for study-related monitoring, Sponsor audits, and IRB/EC review. The study site must also allow inspection by applicable health authorities.

7.5 USE OF COMPUTERIZED SYSTEMS

When clinical observations are entered directly into a study site's computerized medical record system (i.e., in lieu of original hardcopy records), the electronic record can serve as the source document if the system has been validated in accordance with health authority requirements pertaining to computerized systems used in clinical research. An acceptable computerized data collection system allows preservation of the original entry of data. If original data are modified, the system should maintain a viewable audit trail that shows the original data as well as the reason for the change, name of the person making the change, and date of the change.

